#### How the intervention providers are assigned to groups

The treated and control groups are defined at the team level, based on whether or not a team was assigned to be trained in Your Choice. Once a team has been trained at any of the three training stages, it can only act as a treated team in subsequent phases. If a team acts as a control team in one stage, it can be re-randomised in the next stage and possibly become a treated team.

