#### Randomisation

Randomisation across the full study (internal pilot + efficacy)

Randomisation is **at the unit of teams of practitioners**. The rationale for this is that practitioners within the same team interact a lot with each other. Randomisation at the level of the practitioner would therefore create too much of a risk of cross-contamination.

Randomisation is **stratified at the LA level**. This model ensures that there will be trained and control teams in all participating LAs, a configuration that aligns well with the model of funding for delivery of the intervention.

Randomisation happened in three phases, that correspond to three batches of funding for programme delivery mentioned earlier: the Home Office phase (December 2021), the pilot phase (spring 2022) and the efficacy phase (summer 2023). The randomisation procedure was the same at all phases, to ensure continuity and in line with the internal nature of the pilot. Specifically, in an initial step LA put forward a list of so far untrained teams that they have available for delivering Your Choice. Among LAs that have two or more teams available for training, the evaluators randomly select teams for being trained and teams for being controls. The randomisation code is developed in STATA 16. The outcome of the randomisation is communicated to LAs by the evaluators, and the training of selected teams is implemented.

To check adherence to randomisation in the efficacy trial, we will require LAs to provide a list of practitioners in each of the teams involved in the study and to let us know if and when they have been trained ahead of start of delivery in the efficacy phase.

Practitioners will know whether they are part of a treated or control team and therefore cannot be blind to the experimental assignment. When recruiting young people, practitioners will know the young person's experimental condition. This means that the young person may not be blind to the assignment at the time of recruitment. Training of practitioners and SPOCs around recruitment will strongly emphasize the need to recruit young people into the study (as opposed to an experimental arm) and to not divulge their treatment condition.

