#### Teams of practitioners involved in efficacy phase

We provide further details on the 123 teams (type B and type C above) involved in the efficacy phase of the trial and on the randomisation performed to allocate treatment to those teams whose condition could be randomised in this round. Table 3 below breaks down these 123 teams into six types, depending on their status in previous phases of delivery. It shows that 22 teams (of types 5 and 6) cannot be randomised in efficacy because they were randomised into treatment during previous batches of randomisation and so can only continue acting as a treated team in efficacy. Among the other 101 teams (of types 1, 2, 3, 4), randomisation cannot take place in LAs where there is only 1 team of this type. This happens in 6 LAs (Barnet,

Bexley, Havering, Hounslow, Lewisham, Newham). This means that we end up with 95 teams for randomisation in the efficacy stage of the study.

Table 3: Teams involved in the efficacy stage of the evaluation

Type of team	Number of teams
1. New teams (these teams were never included in the HO or pilot batches of randomisation, nor did they recruit any participant in previous phases)	69
2. Teams that were randomised into control during the Home Office phase	3
3. Teams that were randomised into control during the plot phase	28
4. Team that was non-randomly selected as control during the pilot phase	1
5. Teams that were randomised into treatment during the Home Office phase	4
6. Teams that were randomised into treatment during the pilot phase	18
Total	123

As for the pilot phase, the 28 LAs that are participating in the efficacy phase will be required to sign a Grant Agreement with the Violence Reduction Unit outlining the funding they will receive, as well as minimum requirements attached to their participation, including their willingness for their teams to partake in the randomisation, their readiness to share data about participants' background information and compliance with the study, their willingness to facilitate survey data collection, and the readiness to deliver Your Choice during the duration of the pilot.

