Step 3. Main analysis, which will be a linear probability model to measure the impact of Your Choice on an indicator for high to very high conduct problems (primary outcome). The regression will also control for the baseline outcome and any controls for which we find statistically significance imbalances in step 1, as well as Local Authority fixed effects. Standard errors will be clustered at the Local Authority level, following Chaisemartin and Ramirez-Cuellar (2022). Effects will be shown in percentage points and as a percent change relative to the baseline average frequency of young people in the high to very high range for this population. We will show the 95% confidence interval for the estimated effect. This analysis will directly address research question 1.

Step 4. Robustness analysis of estimated effects on primary outcome. This will involve estimating alternative versions of the primary regression model using a post-double selection

LASSO to identify variables that are related with both the treatment status and the primary outcome. We will consider relevant contextual, demographic, personal and environmental information as described in step 1. This analysis will provide further support for the findings in the main analysis (step 3).

Step 5. Steps 3 and 4 will be repeated for the secondary outcomes measuring whether the young person got arrested at any point during the 16 months following recruitment into Your Choice (PNC data), and risk assessments by the young person and practitioner at endline (survey completed at week 20 after recruitment). Effects on arrest probabilities will be shown in percentage points and as a percent change relative to frequency of arrests among the control group over the same period. Effects on risk levels will be shown in standard deviation units. Standard errors will be clustered at the local authority level and we will show the 95% confidence interval for the estimated effect. This analysis will address research question 2.

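### Teams were randomised in three batches with unequal chances of being treated, and the primary model has no batch or phase term

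*Protocol*

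**What the plan says.** The Protocol (Randomisation) describes successive draws: "Randomisation happened in three phases, that correspond to three batches of funding for programme delivery mentioned earlier". The section on assigning providers to groups fixes what happens between draws. For treated teams: "Once a team has been trained at any of the three training stages, it can only act as a treated team in subsequent phases". For controls: "it can be re-randomised in the next stage and possibly become a treated team". Protocol Table 3 and its text give the result for the efficacy phase: "22 teams (of types 5 and 6) cannot be randomised in efficacy because they were randomised into treatment during previous batches". After six single-team LAs are also set aside, "This means that we end up with 95 teams for randomisation in the efficacy stage of the study".

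The Protocol (Analysis) pools teams randomised in all three batches. Its Step 3 model has treatment, the baseline outcome, any covariate found imbalanced, "as well as Local Authority fixed effects". The SAP (Primary outcome analysis) has the same terms with strata fixed effects, and its Design overview names LA as the only stratification variable. Neither document specifies a batch or phase term, a probability weight, or a sensitivity analysis by batch. The SAP notes under Table 5 that earlier batches leave more trained than control teams, but says only that the power calculations allow for it.

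**The concern.** When the chance of treatment differs between randomisation strata, the analysis should condition on those strata. Here the chance depends on when a team was first randomised as well as on its LA. LA fixed effects cannot remove a difference that lies between teams of the same LA. Allowing for unequal arm sizes in the power calculation deals with precision, not with bias.

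The documents give reasons why batch or period could be related to the outcome:

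- LAs chose which untrained teams to put forward at each round, so order of entry is not random.
- Returning young people go back to their previous team, so caseloads of established teams may differ.
- The endline survey procedure changed early in the pilot, and 18-year-olds were added after it.
- Endline attrition in the pilot was 54%, against 30% expected in efficacy, and pilot control teams followed data collection less well.

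The Protocol (Design) defends pooling by the consistency of procedures across periods. That does not address unequal treatment probabilities. At stake is a shift in the primary estimate that more recruitment would not remove.

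**Working it through.** **1. The plan's own counts.** Protocol Table 3: 69 + 3 + 28 + 1 + 4 + 18 = 123 teams. Fixed as treated: 4 + 18 = 22. Remaining: 123 − 22 = 101. Less six single-team LAs: 101 − 6 = 95, as stated. Table 2 effective teams: 66 control + 72 treated = 138, as stated.

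**2. Chance of treatment by batch, efficacy phase.** Under ideal 50-50 draws, an early team is treated with probability 0.5 + 0.5 × 0.5 = 0.75, and a new team with 0.50. From Table 3, earlier-randomised teams number 22 + 3 + 28 = 53, of which 31 are earlier controls.

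- All 31 re-drawn: (22 + 15.5)/53 = 0.71.
- All six single teams were early controls and stayed control: (22 + 12.5)/53 = 0.65.

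The documents do not give the arm or batch of the six single teams.

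**3. What this does to the arms.** The 69 new teams split 34.5 to 34.5 in expectation. Early teams are then 37.5/72 = 52% of treated and 15.5/50 = 31% of control efficacy teams, a gap of 21 points. The gap is 15 to 25 points depending on what the six single teams are.

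**4. Period.** From Table 2, the treated share of teams is 18/37 = 49% in the pilot and 68/123 = 55% in efficacy. The analysis sample is 0.70 × 1,678 = 1,175 efficacy participants plus 83 pilot participants with endline data. If participants split as teams do, pilot participants are about 5.9% of the treated and 7.5% of the control sample. The gap is about 1.7 points, so this part is much weaker than the batch part.

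**5. Bias with LA fixed effects.** The staged draw was simulated with 28 LAs and 123 teams. LA sizes were assumed (21, 12, the rest 9 or fewer, median 3), with about two early teams per LA and 83 pilot observations. The outcome differences are assumptions, and no baseline adjustment was applied.

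| Assumed difference | LA effects only | LA plus batch and phase |
|---|---|---|
| Early vs new teams, 5 points | about 0.7 point | 0 |
| Early vs new teams, 10 points | about 1.4 to 1.7 points across assumed layouts | 0 |
| Pilot vs efficacy period, 30 points | about 0.6 point | 0 |

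**6. Scale.** Scenario 1 minimum detectable effect (MDE): 24% × 0.3 = 7.2 points. Scenario 2: 22% × 0.6 = 13.2 points (the SAP prints 10.8, which is 18% of 0.6). A bias of 0.7 to 1.7 points is 0.7/7.2 = 10% to 1.7/7.2 = 24% of the first, and 0.7/13.2 = 5% to 1.7/13.2 = 13% of the second.

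**The case against.** The best defence is that much of this is already handled. The model is not adjusted for LA alone: the baseline outcome is included and would absorb at least part of any caseload difference between batches or periods. The SAP also admits team characteristics found imbalanced, so batch could enter that way, and a post-double-selection LASSO is planned as a robustness check. This stands as a reason to expect a smaller bias than the table shows. It does not close the gap. Batch is not among the characteristics listed for the balance check, and a known design feature should not depend on a significance test.

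Four stronger readings are tempting, and the documents do not support them:

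- *A 30-point shift between pilot and efficacy.* The SAP's 0.3 comes from baseline and endline pilot data. Its 0.6 is baseline only and pools efficacy with pilot data. These are not endline means by phase.
- *A larger bias, taken from the 21-point gap between arms multiplied by an assumed outcome difference.* That ignores the LA effects, which lowered the figure in these simulations. No passage supports any particular batch difference.
- *Confounding because early teams have delivered for longer.* Longer delivery applies to treated teams only. It is variation in the effect, which batch terms do not remove. Nor did teams simply volunteer early: LAs put them forward, although teams had to consent.
- *A need to replace the planned test by randomisation inference.* In simulation, LA-clustered tests rejected a true null in 5.5 to 6.5% of trials, which does not call for it.

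**Conclusion.** The structural point holds on the documents alone: treatment probability differs by batch within LA (about 0.71 against 0.50; 0.65 to 0.75 under other assumptions), all batches are pooled, and the primary model conditions on neither batch nor phase. Whether this biases the estimate, and in which direction, depends on batch and period differences in the outcome that the documents do not report. The simulated figures are therefore a range under assumptions, including assumed LA sizes, and are upper-side values in that baseline adjustment is left out. The batch part is the main one. The period part is secondary, because pilot participants are only about 83/1,258 = 7% of the planned analysis sample. This should be fixed, since the remedy is cheap and a choice made after results are seen would be open to dispute. It does not invalidate the design.

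**What to change.** In Protocol Step 3 and the SAP primary model, add to the LA fixed effects (i) indicators for the batch of the team's first randomisation and (ii) an indicator for recruitment phase, pilot or efficacy. Include both whatever the balance tests show. State how the six single teams and the one non-randomly selected control team are handled.

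Both terms are needed. In simulation, LA-by-batch cells without phase removed the batch part but left 0.5 to 1.6 points for period differences of 10 to 30 points. Additive indicators remove a batch difference that is common to all LAs. For one that varies by LA, pre-specify full LA × batch × phase cells as a sensitivity analysis.

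Also pre-specify a sensitivity analysis, with LA fixed effects, on efficacy-phase participants of the 95 teams randomised for efficacy. Those teams shared one draw within each LA, so LA effects suffice there.

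Cost: SAP wording and a few lines of code; the evaluators ran each randomisation, so batch and phase should be on record. The simulated standard error rises by about 2% with additive indicators and by about 12 to 20% with full cells, because many small cells contain one arm only. That is why full cells are better kept as a sensitivity analysis. The 95-team analysis drops the 22 fixed teams, the six single teams and the pilot participants, so it is also less precise.

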## Longitudinal follow-ups

No follow-up points have been agreed at this stage.

<sup>16 Ritchie, J. and L. Spencer, Qualitative Data Analysis for Applied Policy Research, in Analyzing Qualitative Data, A. Bryman and B. Burgess, Editors. 1994, Routledge: London.

## Implementation and process evaluation

#### Research questions

The research questions of the implementation and process evaluation (IPE) are:

- 1. To what extent is Your Choice delivered as intended?
- 2. What are the barriers and facilitators to delivery?
- 3. What are young people's and practitioners' views and experiences of Your Choice (acceptability, impacts, and mechanisms)?
- 4. What are practitioners' views on the sustainability of Your Choice?

#### Research methods

To address the above research questions, we will conduct a mixed-methods IPE. We will use a triangulation design convergence model, where quantitative and qualitative data will be collected and analysed separately and then interpreted together to provide complementary perspectives on the same topic.

The quantitative data will involve analysis of session survey forms (tested during the pilot) completed by a practitioner after each session with a young person in both Your Choice and BAU arms.

The qualitative data will focus on the Your Choice arm and will involve recruiting young people (n=16-20), Your Choice trainers (n=8-10), youth practitioners (n=16-20), and other professionals (e.g., multi-agency risk or exploitation panels, service managers) (n=9-12). The sample sizes were determined based on the research team's experience of conducting similar previous studies to achieve diversity in views and perspectives whilst being achievable within the resources of the project. Interviews/focus groups with youth practitioners will be conducted during the mid-stages of the trial. Interviews with young people will be conducted twice, on completion of the programme and approximately six months later, to examine sustainability of short-term changes and any longer-term changes. Topics that will be examined in the interviews/focus groups build on those tested in the pilot. Topics will illustrative example questions include:

- Views and experience of Your Choice
- To what extent does the programme fit with and add to the landscape of existing practice?
- How acceptable is Your Choice?
- What could be done differently to make the sessions better for young people?

## How the programme is implemented

- To what extent does this fit, or not fit, the theory of change and intervention description?
- How, if at all, could the programme be tailored to meet the context and population needs?

## Barriers and facilitators to implementation

- What helps and hinders recruiting young people to the programme and then engaging them?
- Which components of the intervention are more, and less, readily delivered?

## Impact of Your Choice on young people

- Is there evidence to support anticipated outcomes in the logic model?
- Are there any unintended consequences (e.g., due to continued contact with the Youth Justice System)

## Sustainability

• What are professionals' views on how to continue delivery beyond the end of the project?

## **Analysis**

Table 8: IPE methods overview (adapt as necessary)

Research methods	Data collection methods	Participants/ data sources (type, number)	Data analysis methods	Research questions addressed	Implementation/ logic model relevance
IPE	Survey	Session forms completed by the practitioner after each session of Your Choice or BAU	Descriptive statistics and inferential statistics (e.g., t-tests, chi- square, regression) of the session forms (described in the impact	IPE research questions 1 and 2	Intervention description, logic model

			evaluation section; p.39)		
IPE	Interview	16-20 young people (Your Choice arm)	Framework approach and thematic analysis	IPE research questions 1, 3, and 4	Intervention description, logic model
IPE	Interviews/ focus group	Your Choice trainers (n = 8- 10), youth practitioners (n = 16-20), and other professionals (e.g., multi- agency risk or exploitation panels, service managers) (n = 9-12)	Framework approach and thematic analysis	IPE research questions 1, 3, 4, and 5	Intervention description, logic model

*Note.* IPE = implementation and process evaluation.

The quantitative data will be analysed to answer IPE research questions 1 and 2:

#### 1. To what extent is Your Choice delivered as intended?

Using descriptive statistics, we will examine the number and type of sessions and duration of support in the Your Choice arm, which will be compared with the intervention description.

#### 2. To what extent is delivery of Your Choice different, and similar, to BAU?

We will run similar descriptive statistics for the BAU arm. We will then conduct inferential statistics (e.g., t-test, chi-square tests) to examine differences in the number and type of sessions and duration of support between Your Choice and BAU using the process data and workbook data.

Qualitative data (i.e., transcripts, free-text responses) will be analysed using the NVivo qualitative data analysis software. We will use the framework analysis approach to manage

\_

<sup>16 Ritchie, J. and L. Spencer, Qualitative Data Analysis for Applied Policy Research, in Analyzing Qualitative Data, A. Bryman and B. Burgess, Editors. 1994, Routledge: London.

the data, categorising transcripts according to which component of the logic model they address. We will then use thematic analysis  to analyse the data organised in the framework to explore themes across participants' experiences and perspectives. At least two members of staff (including the peer researcher) will be involved and there will be regular coding review meetings throughout the stages of the analysis. Themes will be identified using inductive and deductive approaches, drawing on the logic model but also any new themes or ideas that are present in participant responses. Such approaches are commonly used in applied policy evaluations. Different reliability processes are available for qualitative data than quantitative data, and the research team will adhere to quality standards for establishing the trustworthiness of the data (i.e., credibility, transferability, dependability, and confirmability). 

The qualitative data will be used to address IPE research questions 1, 3, 4, and 5:

- 1. To what extent is Your Choice delivered as intended?
- 3. What are the barriers and facilitators to delivery?
- 4. What are young people's and practitioners' views and experiences of Your Choice (acceptability, impacts, and mechanisms)?
- 5. What are practitioners' views on the sustainability of Your Choice?

Young people's and practitioners' descriptions of Your Choice will be integrated with the quantitative data and intervention descriptions. This will enable us to, for example, gain some understanding of why there might be differences in the quantitative data between what was delivered and what was expected based on the intervention description. Understanding of barriers and facilitators to delivery will also enable us to further understand what was delivered and why it was delivered that way.

Young people's and practitioners' views and experiences of Your Choice in relation to acceptability, impacts, and mechanisms of change will be interpreted with, and complement, data from the overall quantitative efficacy trial on outcomes and mechanisms. Practitioners' views on the sustainability of Your Choice, and barriers and facilitators to sustainability, will provide evidence to inform potential plans for the continued delivery and scale up of Your Choice.

One of the outputs of the qualitative component will be vignettes, co-produced with the Youth Advisory Panel, based on participants' collective experiences of the programme. The

-

<sup>17 Braun, V. and V. Clarke, Using thematic analysis in psychology. Qualitative Research in Psychology, 2006. 3(2): p. 77-101.

<sup>18 Yardley, L., Dilemmas in qualitative health research. Psychology & Health, 2000. 15(2): p. 215-228.

aim of these vignettes is to articulate young people's journey through the intervention. These will be used to help communication about the key aspects and findings of the project in accessible ways for public-facing dissemination (e.g., public summaries). A purpose of the vignettes is to help anchor the evaluation findings to the views and experiences of the young people.

In the final report, we will integrate findings from the quantitative and qualitative components of the full trial, which involves collecting complementary quantitative and qualitative data on the topic to answer the research questions. We will use meta-matrices to integrate findings, which involve summarising findings from different data sources according to the research question they address.

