Session forms: Practitioners are requested to fill out a session form every time they conduct a session with the young person or every time a session is cancelled. The session form asks a few details about the location of the session, the young person's level of engagement, whether the session was related to the Your Choice programme, and depending on the latter offers one or two dropdown menus to describe the content of the session. The practitioner is then offered a free text box to include any further comments on the session. If the session did not take place, the session form asks whether the reason for cancellation is known and offers a free text box to include any other details about the session that did not take place.

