#### **Analysis**

Our primary analysis uses only randomised teams during the Home Office, pilot and efficacy phases. It will involve various steps.

Step 1. Thorough check that the group of young people assigned to Your Choice appear to come from the same population as those assigned to the control group along many observed variables describing demographic characteristics (e.g. gender, age, ethnicity, etc), main activity at baseline (education or training, employment, other), whether looked after, special education needs, primary needs for Local Authority support (e.g. abuse, disability, family acute stress, etc), various measures observed in the baseline youth survey including SDQ scores and self-reported risk assessment, practitioner risk assessment from baseline practitioner questionnaire. We will also check that the distribution of services to which young people have been assigned look balanced across experimental arms. All subsequent analysis addressing the key research questions set out earlier in this document must rely on a good understanding of the comparability between the treated and control groups.

Step 2. Thorough check of the delivery of Your Choice in contrast with BAU, revealing the extent to which the programme effectively changes interactions between the youth workers and young people and characterising the intensity of treatment for different groups. Specifically, we will check that young people assigned to Your Choice received an intensive schedule of meetings with content that is specific to the programme (hence matching the Your Choice protocol), while young people assigned to the control teams did not. Again, all subsequent analysis and interpretation of findings must rely on a good understanding of what the programme delivers in comparison with BAU.

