#### Primary population of interest

The primary population of interest will be young people aged 11-18 referred to their Local Authorities for support and at medium to high risk of contextual harm.

Table 5 provides information about the number of young people and teams, and their distribution across treated and control groups, which were used to perform the power calculations. These numbers reflect the best information available at the time of writing, drawn from the Local Authorities' plans in terms of teams and expected numbers of participants in each team, before the trial started (sample A) and when the decision to extend the recruitment period was considered (Sample B).

Sample A reflects the size and composition of the final sample as estimated before the trial started. It totals 1857 young people across 138 teams.

Sample B reflects the size and composition of the final sample as re-estimated as of January 2025. It totals 1563 young people across 132 teams. This number was re-estimated based on recruitment to date and new information from Local Authorities about the number of young people they would expect to recruit if the recruitment period was extended to the end of February 2025.

		Sample A (1.0 original version)	Sample B (1.1 January 2025 update)
Average cluster size (if clustered)		Average number of participants per cluster (team): 13	Average number of participants per cluster (team): 11.8
Number of clusters (teams)	Intervention	70	83
	Control	70	49
	Total	138	132
Number of participants	Intervention	960	937
	Control	897	626
	Total	1857	1563

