We will further extend our analysis by using an Instrumental Variable (IV) approach to give an indication of the effects a) of receiving Your Choice and b) of the intensity of treatment. To implement a) and b), we will use a Two Stage Least Squares (2SLS) approach with group allocation as the instrumental variable for compliance. In a), we will define compliance as a binary indicator that takes the value 1 if the young person receives any of the Your Choice programme and 0 otherwise. In b), we will define compliance as a continuous variable measuring the proportion of Your Choice sessions that the young person received out of the total planned for participants (=12x3). The first stage will model the compliance variable using the same explanatory variables used for the headline ITT analyses and the instrument. The second stage model will use predicted compliance in place of the group identifier variable in the ITT analyses specified above to generate Complier Average Causal Effect (CACE) estimates.

At the practitioner level – practitioners are supposed to received 3 + 1 days of training and to receive clinical supervision at least once monthly. Using information from the workbook on training and clinical supervision sessions, we will document the extent to which this happened across teams involved in the trial. We will not take this form of compliance into consideration in the estimation of the treatment effects.

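### The tests named for comparing Your Choice and BAU delivery make no allowance for team randomisation or repeated sessions, so used as named they give standard errors that are too small

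*Protocol*

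**What the plan says.** The comparison is question 2 as numbered in the Protocol's Implementation and process evaluation, Analysis: how far delivery of Your Choice differs from BAU. (The research-question list earlier in that chapter numbers its items differently and does not contain this one.) The text there reads: "We will then conduct inferential statistics (e.g., t-test, chi-square tests) to examine differences in the number and type of sessions". It adds duration of support and names process and workbook data as the sources. Table 8 gives the methods as "Descriptive statistics and inferential statistics (e.g., t-tests, chi- square, regression) of the session forms". Neither place mentions team, Local Authority (LA) or repeated sessions, and neither states the unit of analysis or a significance level.

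Four other parts of the documents bear on this:

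- **Randomisation (Protocol).** Teams are the unit because "practitioners within the same team interact a lot with each other".
- **Data (Protocol).** "Practitioners are requested to fill out a session form every time they conduct a session with the young person", so one young person contributes many forms.
- **Impact evaluation, Analysis, Step 2 (Protocol).** Of the delivery contrast it says that "all subsequent analysis and interpretation of findings must rely on a good understanding of what the programme delivers in comparison with BAU".
- **Clustering elsewhere.** LA-clustered standard errors are specified for the primary, secondary and mechanism analyses (Protocol Steps 3, 5 and 6; SAP, Primary outcome analysis) and for the missingness models (SAP, Missing data). The SAP's section on intervention content is descriptive. It names no test and does not withdraw the Protocol's tests.

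**The concern.** A two-sample t-test and a chi-square test take their standard error or null distribution from independent observations. Here arm is assigned to whole teams. Young people in one team share practitioners, supervision and habits of work, so their delivery measures are likely to be correlated. If session type is tested form by form, forms from one young person are correlated as well. Both features make the real variance of the arm difference larger than the test assumes.

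At stake is the delivery contrast that Step 2 makes a condition for interpreting the results. Several delivery features will be compared. A feature that Your Choice does not change could then be reported as a significant difference from BAU more often than the nominal level implies.

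**Working it through.** **Inputs.** From the SAP, Primary population of interest, January 2025 sample: "It totals 1563 young people across 132 teams" and "Average number of participants per cluster (team): 11.8". Check: 1563/132 = 11.84, which reproduces the stated 11.8. The treated arm is planned to receive 12 × 3 = 36 sessions (SAP, Compliance). The documents give no ICC for delivery. The SAP's 0.09 (0.12 in the original scenario) is for the SDQ outcome and is only illustrative here. A two-sided 5% level is assumed.

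**One value per young person** (number of sessions, duration). Only team and LA clustering applies. With m = 11.8:

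- Design effect: DE = 1 + (m − 1) × ICC
- True type I error of the unadjusted test: 2 × [1 − Φ(1.96/√DE)]

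| Team ICC (assumed) | DE | True type I error |
|---|---|---|
| 0.02 | 1 + 10.8 × 0.02 = 1.22 | 7.6% |
| 0.05 | 1.54 | 11.4% |
| 0.09 | 1.97 | 16.3% |
| 0.12 | 2.30 | 19.6% |
| 0.30 | 4.24 | 34.1% |

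At ICC 0.09, the 1563 young people carry the information of 1563/1.97, or about 793.

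**Simulation check.** With 132 teams in 29 LAs and no arm difference, the unadjusted t-test rejected 7%, 12%, 17%, 20% and 35% of the time at these five ICCs. A separate run of 1,500 replicates at ICC 0.05, 0.09 and 0.12 gave 11%, 17% and 21% with equal team sizes. With team sizes varying at an assumed coefficient of variation of 0.6, it gave 13%, 20% and 25%. On the same data, regression with LA fixed effects and LA-clustered standard errors rejected 4.4% to 5.6% of the time.

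**Where the variance sits.** The plan's own power simulation places its ICC at LA level, and the Protocol's control condition says BAU varies between LAs. If all of a 0.12 ICC lies between LAs and each LA has a similar treated share (about 63%, from 83/132 teams), the unadjusted t-test rejects about 5-6% of the time. If the 0.12 is split equally between LA and team, it rejects about 13%.

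**One row per session** (one possible unit for session type). With k sessions per young person, DE = 1 + (k − 1) × ρ_person + (m − 1) × k × ρ_team. All inputs below are assumed:

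- k = 12, ρ_person = 0.1, ρ_team = 0.02: DE = 1 + 1.1 + 2.6 = 4.7, type I error about 37%.
- k = 36, ρ_person = 0.3, ρ_team = 0.09: DE = 1 + 10.5 + 35.0 = 46.5, type I error about 77%.

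**The case against.** The strongest reply is that the plan does not commit itself to unadjusted tests. They are given as examples, Table 8 includes regression, and the evaluators cluster routinely, even in the missingness models. That stands: a correct analysis is not excluded, only left unspecified. A reader might infer that a wrong method has been fixed, or that clustering is reserved for the impact outcomes. The documents support neither.

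A second reply is that the SAP's compliance analysis already models session dose. Its first stage regresses the proportion of planned sessions on allocation, with the headline covariates, which include strata fixed effects. This helps for dose, but it does not restate the level of the standard errors and does not cover session type or duration.

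Third, the size of the problem is unknown. A reader might infer from the table that the error rate is several times nominal. That is not established, because it depends on a team-level delivery ICC that the documents do not give, and inflation is slight if variation lies between LAs. The session-level figures rest wholly on assumed inputs.

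Fourth, the reach is limited. The question whether Your Choice is delivered as intended is answered descriptively, and Step 6 tests mechanisms on secondary outcomes with LA-clustered errors. The pilot already reported a more intense schedule under Your Choice, so a large contrast in session numbers may well remain significant after adjustment.

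**Conclusion.** The point holds as a gap in specification. The tests named for the delivery comparison do not fit the design, and nothing elsewhere in the documents supplies the adjustment. Followed literally, they give standard errors that are too small and too many false positives when delivery varies between teams. For young-person-level measures, a nominal 5% becomes about 7-8%, 11-12%, 16-17%, 20% and 34-35% at team ICCs of 0.02, 0.05, 0.09, 0.12 and 0.30. These figures assume equal teams of about 12; unequal teams make them somewhat worse. If variation is only between LAs, with similar treated shares in each, the rate stays near 5-6%.

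It would be too strong to say that differences between teams are turned into an apparent programme effect. With teams randomised, ignoring team clustering affects the standard error and does not by itself bias the estimated difference. The consequence is confined to the Your Choice versus BAU delivery contrast used in Step 2. The primary and secondary outcome analyses, the descriptive fidelity question and the Step 6 mechanism analysis are not affected.

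**What to change.** In the Protocol's process evaluation Analysis (question 2 and Table 8), replace the example tests with a stated model, and carry it into the SAP's section on intervention content:

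1. Collapse session forms to one row per young person: number of sessions, share of sessions of each type, and weeks of support. State how young people with no forms are handled.
2. Regress each measure on assigned arm with LA fixed effects and LA-clustered standard errors, as the SAP already does for the primary outcome and the missingness models.
3. Report each difference with its 95% confidence interval.

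If session-level rows are kept for session type, use a model that accounts for both young person and team.

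The cost is a change of wording and a few lines of code, with no new data. Intervals will be wider and p-values larger than from the unadjusted tests.
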